## **3.0 STUDY DESIGN**

### **3.1 Description of the protocol**

This study is designed randomized controlled, 2 arm parallel group pilot study.

### **3.2 Duration of study participation**

The estimated study duration for each participant in this study is 24 week. The duration of the protocol was selected based on recommendation from the American College of Sports Medicine's Guide to Exercise and Cancer Survivorship for aerobic exercise prescription.

### **3.3 Interim analysis**

Interim analysis will be performed once all participants have completed the 12th week of the project. This analysis will be done on the efficacy and safety of the intervention. We will do a between group comparison of circulating biomarkers and a review of adverse events (see section 8.1 for full analysis plan).

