## **5.0 DESCRIPTION OF INTERVENTION**

**5.1 Home-based exercise program.** The intervention will include a combination of both aerobic and body-weight based exercises. The aerobic portion of the intervention will include 5 days of light to moderate intensity walking for 30 mins (weekly total of 150 mins). Intensity will be set at 40-60% of the individual's heart rate reserve using the Karvonen formula (Exercise HR = % of target intensity ( $HR_{max} - HR_{rest}$ ) +  $HR_{rest}$ ). Participants

will be given their targeted HR range by the PI and will be taught how to palpate and calculate HR prior to the beginning of the program. The body-weight based exercises will be done 3 times a week. Exercises will consist of 3 sets of 15 reps of bodyweight squats, incline push-ups, and hip thrusts. If these exercises cannot be performed, lower intensity exercises such as sit-to-stand, wall push up and pelvic tilt can be replaced. These exercises are aimed at increasing strength and endurance of the major muscle groups of the body. Individuals in this group will be given a pocket guide with instructions on how to safely perform the exercises and document the completion of the exercises.

**5.2 Waitlist-Control Group.** Participants assigned to this group will be asked to maintain normal activity and visit the CTRC fitness center for research appointments.

**5.3 Method of assigning patients to intervention group.** Patients eligible to participate in this study will be allocated to either the exercise group or wait-list control group (1:1) based on a pre-specified randomization list

Example:

**Set #1:** 2, 1, 2, 2, 1, 2, 2, 2, 1, 1, 2, 2, 2, 1, 2, 1, 2, 2, 2, 1, 1, 1, 1, 2, 2, 1, 2, 1, 2, 2

1: Control Group; 2: Intervention Group

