## 7.0 STUDY PROCEDURES

### 7.1 Visit schedule

Patients will be asked to attend 4 visit with the study investigators. Description of each visit is detailed below.

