## **8.0 STATISTICAL CONSIDERATIONS**

### **8.1 Statistical analysis plan**

Analysis will be done after all participants have completed the 12-week and 24-week timepoints, respectively. The interim analysis at 12-weeks will be for safety and efficacy of the intervention and will include a between group comparison of circulating biomarkers and a review of adverse events reported by study participants.

Statistical analysis will be performed using IBM SPSS 19.0 software. A 2 group analysis of variance (ANOVA) will be used to compare changes in biomarkers, physical function, body composition, body density, and quality of life between the exercise group and the WLC. Pearson's Product Moment Correlation will be used to measure associations between biomarkers in Aim 1 to body composition, body density, physical function and quality of life measured in aim 2. A value of  $p < 0.05$  will be considered statistically significant. The results of this study will be used to calculate power and determine sample size for future research questions in this field.

We will also evaluate the projects procedures and timeline for feasibility. We will document and review our timelines for recruitment for this pilot and ask participants to comment on their experiences in this project with pointed efforts to understand ways to improve the project procedures for effectiveness and efficiency. We will also assess feasibility by documenting and reviewing study patient description described below.

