#### 9.1.1 Monitoring Safety

Due to the low risk associated with participation in this protocol, The Principal Investigator will conduct independent review and report any findings to the CTRC Data Safety Monitoring Committee (DSMC) and the UTHSCSA IRB. It is not anticipated that any safety issues will arise from this study because it is a low risk interventional exercise study.

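### The week-12 between-arm marker comparison has no decision rule, alpha allocation or restricted audience, and falls while later-enrolled men still have outcome visits ahead

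*Combined protocol and SAP*

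**What the plan says.** Section 3.3 fixes the timing: "Interim analysis will be performed once all participants have completed the 12th week of the project". It gives the purpose, "This analysis will be done on the efficacy and safety of the intervention", and the content: "We will do a between group comparison of circulating biomarkers and a review of adverse events". It refers to 8.1 for the full plan.

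Section 8.1 repeats the purpose ("The interim analysis at 12-weeks will be for safety and efficacy of the intervention") and sets two analysis times: "Analysis will be done after all participants have completed the 12-week and 24-week timepoints, respectively". It specifies a two-group ANOVA on changes, with significance at p<0.05. It gives no boundary, no action that depends on the result, no division of alpha between the two times, no primary time point, and no statement of who may see the week-12 result. The use it states for the results is planning future research.

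On contact with participants, 7.1 says "Patients will be asked to attend 4 visit with the study investigators", and under 5.1 exercisers "will be given their targeted HR range by the PI". Section 6.0 lets investigators withdraw a man when they judge it to be for his benefit. Under 7.3, the 6-minute walk, SF-36 and FACIT-F are collected at baseline and week 24 only. Skinfolds and blood are taken at baseline and at weeks 12, 18 and 24. Blinding is not mentioned.

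On safety, 9.1.1 says "The Principal Investigator will conduct independent review and report any findings" to the CTRC DSMC and the IRB.

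**The concern.** The comparison is timed by the last man's week-12 visit, not by the end of follow-up. Men enrolled shortly before him, and he himself, then still have week-24 visits ahead, and some have week-18 visits too. The text has the study team producing the result, and nothing keeps it from staff who remain in contact with those men.

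A team that has seen which arm is ahead may encourage exercisers differently, speak differently to controls about the programme, or use its discretion over withdrawal differently. It may also conduct the walk test and skinfolds differently. For these men the only post-baseline walk test, SF-36 and FACIT-F would be collected after the result is known, whereas men who had already finished gave theirs before. Adherence and retention, which are feasibility outcomes under 8.2, are open to the same influence.

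There is also a plain multiplicity question. The same markers are tested at p<0.05 at week 12 and again at week 24, and the plan does not say which result is the finding. Against these costs, the plan names no decision that the week-12 efficacy result would inform.

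**Working it through.** The plan gives no power calculation, interim boundary, overall alpha or accrual period for this analysis, so there is no figure of its own to reproduce. Two quantities can be worked out under stated assumptions.

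**1. Men still in follow-up when the interim is triggered**

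Inputs: 30 men (4.1); interim when the last man reaches week 12 (3.3); visits at weeks 12, 18 and 24 (7.3). Assumption: accrual is uniform over *A* weeks, with man *i* (*i* = 0 to 29) entering at *iA*/29.

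The interim falls at calendar week *A* + 12. Man *i* still has his week-24 visit ahead if *iA*/29 + 24 > *A* + 12, that is, if *i* > 29(*A* − 12)/*A*. He also has his week-18 visit ahead if *i* > 29(*A* − 6)/*A*.

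Example, *A* = 26: 29 × 14/26 = 15.6, so men 16 to 29 qualify, which is 14 men. For week 18, 29 × 20/26 = 22.3, so men 23 to 29 qualify, which is 7 men.

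| Assumed accrual (weeks) | Week-24 visit ahead | Week-18 visit also ahead |
|---|---|---|
| 4 | 30 | 30 |
| 12 | 29 | 15 |
| 26 | 14 | 7 |
| 52 | 7 | 4 |
| 78 | 5 | 3 |
| 104 | 4 | 2 |

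These are upper limits, because they treat the result as known on the day of the trigger. Under 7.4.1 serum is frozen until analysis, so assay and analysis time must be added. With a lag of *L* weeks the week-24 condition becomes *i* > 29(*A* − 12 + *L*)/*A*. For *A* = 26 and an assumed *L* = 4, 29 × 18/26 = 20.1, so men 21 to 29 qualify: 9 men instead of 14. With *L* = 12 the condition is *i* > 29 and nobody is left. The one-week visit window in 8.3 is ignored.

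**2. False-positive risk for one marker tested at both times**

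Inputs: p<0.05 at each look (8.1), taken as two-sided. Assumptions: the two test statistics are bivariate normal with correlation *r*, which the plan does not give, and significance at either look may count as a finding.

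Risk = 1 − P(|Z₁| < 1.96 and |Z₂| < 1.96). At *r* = 0 this is 1 − 0.95² = 0.0975.

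| *r* | Risk |
|---|---|
| 0 | 0.0975 |
| 0.5 | 0.0907 |
| 0.8 | 0.0781 |
| 0.9 | 0.0704 |

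With a single designated time point the risk is 0.05.

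For context, the five primary markers in 2.1, if independent, give 1 − 0.95⁵ = 0.226 at one time point. Adding the second look raises this to about 0.34 to 0.38 for *r* from 0.8 to 0.5, and to 1 − 0.95¹⁰ = 0.401 at *r* = 0. The 0.226 comes from having five markers and would remain after the interim is dealt with.

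The size of the behavioural bias cannot be calculated from the documents.

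**The case against.** Several points on the other side have weight.

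- **The look may serve safety.** A reader might infer that the week-12 marker comparison adds nothing but bias. The text does not support that. Section 8.1 states a joint safety and efficacy purpose without assigning the markers to efficacy alone, and 1.1 describes them as reflecting tumour advancement or regression. An unfavourable difference could be read as a safety signal. This stands, and the fix allows for it.
- **Who sees what is partly inference.** It is tempting to say that the same people prescribe the exercise, assess the men at every visit and review interim efficacy. The principal investigator's review in 9.1.1 concerns safety only, and 7.1 refers just to study investigators. What the text supports is narrower: the study team does the comparison and no limit on access is stated. Open-label status is likewise inferred from the design.
- **The primary outcome is a laboratory result.** The five markers are measured in stored serum, so knowledge of arm results can reach them only through behaviour, adherence or withdrawal. The walk test and skinfolds fall under other objectives in 2.3, and SF-36 and FACIT-F under no stated objective. This stands and limits the importance of the point.
- **Expectation is already present.** Participants know their arm and 2.1.1 states a hypothesis of benefit, so these measures are open to expectation bias without any interim. That is true, and the extra effect of seeing an estimate cannot be isolated. It is nonetheless an extra effect that can be avoided at little cost.
- **It is a pilot.** The results are meant to inform later sample sizes, so distortion would carry forward. Pilot status weakens the case for elaborate alpha control, but not for deferring a comparison that has no use in mid-trial.

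**Conclusion.** The point holds as a modest improvement to make, not as a flaw that invalidates the trial. The plan schedules a between-arm marker comparison by the study team with no decision, alpha allocation or restricted audience, before all outcome visits are complete.

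The number of men exposed depends on an accrual period that the plan does not give. Under uniform accrual over 4 to 104 weeks it runs from 30 down to about 4 of 30 at the trigger, before any allowance for assay time; a lag of 12 weeks or more would remove the exposure. The outcomes most at risk are the week-24 walk test, skinfolds, SF-36 and FACIT-F, with adherence and withdrawal.

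The rise in false-positive risk to about 0.07 to 0.0975 for one marker is conditional. It applies only if a week-12 result may be claimed as a finding, which the plan neither permits nor rules out. A reader might take it as an established inflation of the trial's error rate; the documents do not go that far.

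**What to change.** In 3.3 and 8.1:

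1. Limit the week-12 interim seen by the study team to the adverse-event review.
2. Run the week-12 between-group marker comparison after the last Visit 4 and data lock, and label it secondary to the week-24 comparison. The samples and the estimate are the same, so no information is lost.
3. If an unblinded marker look is wanted at week 12 for safety, send it only to the existing DSMC, and state that no efficacy claim will be based on it.

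The cost is a small change to protocol and SAP wording, which 9.1.2 requires to be reported to the research team. The team also waits about 12 more weeks (24 − 12) for the week-12 marker result. No visit, sample or assay is added.

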## **4.0 SELECTION OF PATIENT**

### **4.1 Number of patients planned**

This study plans to enroll 30 men with prostate cancer under active surveillance with 15 men in each arm.

### **4.2 Inclusion criteria**

- men aged 40 years or older
- diagnosed with prostate cancer
- under active surveillance
- Subjects willing and able to provide consent to participating in the study.

### **4.3 Exclusion criteria**

- severe cardiac disease (New York Heart Association class III or greater)
- angina
- severe osteoporosis
- uncontrolled hypertension (blood pressure > 160/95mm Hg)
- uncontrolled sinus tachycardia (> 120 beats per minute)
- uncontrolled congestive heart failure third-degree atrio-ventricular heart block, active pericarditis or myocarditis, recent embolism, thrombophlebitis, deep vein thrombosis, resting ST displacement (> 3mm), uncontrolled diabetes, uncontrolled pain, cognitive impairment, history of falls due to balance impairment or lost of consciousness,
- severe neuromusculoskeletal conditions that limit their ability to perform walking exercise (including ataxia, peripheral or sensory neuropathy, unstable bone lesion, severe arthritis, lower limb fractures within 6 months, lower limb amputation).

## **5.0 DESCRIPTION OF INTERVENTION**

**5.1 Home-based exercise program.** The intervention will include a combination of both aerobic and body-weight based exercises. The aerobic portion of the intervention will include 5 days of light to moderate intensity walking for 30 mins (weekly total of 150 mins). Intensity will be set at 40-60% of the individual's heart rate reserve using the Karvonen formula (Exercise HR = % of target intensity ( $HR_{max} - HR_{rest}$ ) +  $HR_{rest}$ ). Participants

will be given their targeted HR range by the PI and will be taught how to palpate and calculate HR prior to the beginning of the program. The body-weight based exercises will be done 3 times a week. Exercises will consist of 3 sets of 15 reps of bodyweight squats, incline push-ups, and hip thrusts. If these exercises cannot be performed, lower intensity exercises such as sit-to-stand, wall push up and pelvic tilt can be replaced. These exercises are aimed at increasing strength and endurance of the major muscle groups of the body. Individuals in this group will be given a pocket guide with instructions on how to safely perform the exercises and document the completion of the exercises.

**5.2 Waitlist-Control Group.** Participants assigned to this group will be asked to maintain normal activity and visit the CTRC fitness center for research appointments.

**5.3 Method of assigning patients to intervention group.** Patients eligible to participate in this study will be allocated to either the exercise group or wait-list control group (1:1) based on a pre-specified randomization list

Example:

**Set #1:** 2, 1, 2, 2, 1, 2, 2, 2, 1, 1, 2, 2, 2, 1, 2, 1, 2, 2, 2, 1, 1, 1, 1, 2, 2, 1, 2, 1, 2, 2

1: Control Group; 2: Intervention Group

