### 7.2 Pre-screening procedures

Study subjects will be recruited from patients population treated at the University of Texas Health Science Center at San Antonio's Medical Arts and Research Center Urology Clinic. Medical records will be reviewed to determine eligibility. Eligible participants will be mailed recruitment materials and asked to call the investigators if interested in participating in the study. Also, eligible participants will also be approached during regularly scheduled clinic appointments and introduced to the study. Only interested participants will be enrolled into the study.

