### 7.3 Description by type of visit

7.3.1 Visit 1 (Baseline Visit) – This will be the first visit in this study and should last about 30-45 minutes. At this session, we will review the consent form, explain the purpose and procedures of the study, ask the subject to sign the consent form if you agree to participate in the study, and randomly assign the subject to one of the two groups mentioned above. Following this, the following things will happen:

1. Assignment of a Nike FitBit – Each participant, no matter which study arm, will be provided with a Nike Fitbit during the 6 month program. The FitBit will monitor activity and will assist the research team in tracking activity and sleep habits. We will instruct subjects on the use and care of the FitBit.
2. Blood Draw –15 mL of blood (two tubes or 1 tablespoon or 3 teaspoons) to measure circulating markers (PSA, PSMA, EPCA, uPA and uPAR) and circulating tumor cells.
3. Saliva Collection – we will collect about 4 mL of saliva (1/4 of a tablespoon or 3/4 teaspoon) to measure FBI concentrations in saliva.
4. Surveys for Quality of Life and Fatigue – subjects will be asked to complete 2 surveys that will take about 5 minutes to complete. These surveys are:
  - a. Health-Related Quality of Life (SF-36) – this survey will assess subject's overall health status, including physical functioning, role functioning, bodily pain, general health, vitality, social functioning, mental health and emotional health.
  - b. Functional Assessment of Chronic Illness – Fatigue (FACIT-F) – This survey evaluates the impact of fatigue in men with prostate cancer.

5. Body Composition, Body Mass Index and Body Density – will measure body fat percentage by measuring skinfold thickness at 3 sites (chest, abdomen, thigh). Body density will be measured using body fat percentage plus the addition of waist and arm circumference. Body mass index will be calculated by collecting by height and weight measurements from the subjects.
6. 6 minute walk test –overall physical function will be measured using the 6 minute walk test. We will track the distance traveled and use this as baseline score.

7.3.2 Visit 2 and Visit 3 (12 week and 18 week visit) – the following activities will be done at the 12 week and 18 week visit:

1. Blood Draw – we will collect 10 mL (2 teaspoons) to measure circulating markers (PSA, PSMA, EPCA, uPA and uPAR). Note: This is different than at baseline and final visit to quantify circulating tumor cells.

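### Section 5.3 prints a coded 30-entry example sequence and no allocation concealment is described, so those enrolling men could know the next arm in advance

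*Combined protocol and SAP*

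**What the plan says.** Section 5.3 states that eligible patients "will be allocated to either the exercise group or wait-list control group (1:1) based on a pre-specified randomization list". Under an example label it prints a sequence called Set #1, which begins "2, 1, 2, 2, 1, 2, 2, 2, 1, 1, 2, 2, 2, 1, 2, 1, 2, 2, 2, 1" and runs to 30 entries. The key follows: "1: Control Group; 2: Intervention Group".

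Section 4.1 gives the target: "This study plans to enroll 30 men with prostate cancer under active surveillance with 15 men in each arm".

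Section 7.2 describes two recruitment routes. By mail: "Eligible participants will be mailed recruitment materials and asked to call the investigators if interested in participating in the study". In clinic: "eligible participants will also be approached during regularly scheduled clinic appointments and introduced to the study". The clinic sentence does not say who makes the approach, and the record review is also in the passive voice.

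Section 7.1 places all four visits with the study investigators. In Section 7.3.1 the study team, writing in the first person plural, goes through consent at Visit 1 and will then "randomly assign the subject to one of the two groups mentioned above". Baseline blood, saliva, surveys, body composition and the 6-minute walk come after that step.

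The document does not say who generates or holds the list, or how an assignment is released. It mentions no envelopes, central or electronic allocation, or restricted access.

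**The concern.** Randomisation protects the comparison only if whoever decides when and whether to enrol a man cannot foresee his arm. Here a fixed list exists, a coded sequence of full trial length sits in a document the study team holds, and nothing is said about hiding the working list. Someone who could read the next entry might put more effort into a fit, keen man when it is exercise and defer a reluctant man to a control entry, without breaking any written rule.

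The arms could then differ in fitness, motivation or disease course before the programme starts. Men necessarily know whether they are exercising or waiting, so the trial is open-label, and only 30 are planned. The marker, walk-test, adherence and retention comparisons are all exposed. Section 8.1 plans a two-group ANOVA of changes and names no baseline covariate. It also intends to use the results to size later studies, so any bias would carry forward.

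**Working it through.** **1. The printed sequence against the plan's own figures (Sections 4.1 and 5.3).**
- Entries: 30. Planned enrolment: 30. The total agrees.
- Coded 1 (control): 12. Coded 2 (exercise): 18. The plan is 15 and 15, so each arm is off by 3 and the split does not agree.
- It does not balance in successive blocks of 2, 4, 6 or 10, or over all 30.
- Under unrestricted 1:1 allocation, the two-sided probability of a split at least as uneven as 18:12 is 2 × 0.181 = 0.36. It looks like an ordinary unrestricted list. That neither shows nor excludes that it is the working one.

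**2. Who does what (Sections 7.1 to 7.3.1).**

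| Step | Who, according to the text |
|---|---|
| Record review | not stated |
| Clinic approach | not stated |
| Calls from mailed men | the investigators |
| Consent, Visit 1 | the study team |
| Assignment, Visit 1 | the study team, after consent |
| Holding the list | not stated |

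Consent precedes assignment, but that order gives no protection if the list can be read beforehand.

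**3. How predictable the next arm is.** A list that can be read gives 100% correct guesses. A concealed unrestricted list gives 50%. For a concealed blocked list, the expected share of correct guesses by someone who knows past assignments and the block size, and always guesses the arm that is behind, is as follows (block sizes are assumptions):

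| Block size | 2 | 4 | 6 | 10 | 30 |
|---|---|---|---|---|---|
| Correct guesses | 75% | 71% | 68% | 65% | 60% |

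**4. A hypothetical size.** Suppose a fraction f of each arm is steered. Those steered to exercise come from the upper half of a standard normal trait and those steered to control from the lower half, sorted without error; the rest are average. The mean of the upper half is 0.798, so the expected arm difference is 2 × 0.798 × f ≈ 1.6f SD.
- f = 10%: 0.16 SD
- f = 20%: 0.32 SD
- f = 30%: 0.48 SD

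For comparison, the chance SD of an arm difference in any standardised trait at 15 per arm is √(1/15 + 1/15) = √(2/15) = 0.37 SD. The first two scenarios fall below it and the third above. Chance imbalance has no preferred direction, whereas steering does.

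These figures describe a trait, not an outcome. The bias in a change score is the trait difference scaled by how strongly the trait relates to change. The documents give neither f nor that relation.

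**5. Precision is not the issue.** Relative efficiency of 12:18 against 15:15 is (2/15) ÷ (1/12 + 1/18) = 0.133 ÷ 0.139 = 0.96.

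**The case against.** The strongest reply is that silence is not openness. The protocol names no list holder, so it does not say that recruiters hold or see the list. A reader might infer from Section 7 that one team reviews charts, picks men, consents and assigns with the list in hand. The text supports only part of that: the investigators take calls, and the study team consents and assigns. Record review and clinic approach have no named actor, no discretion among eligible men is granted, and mailed men call when they choose.

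A reader might also infer that the printed sequence is the live one, so that every protocol holder knows every assignment. The example label, the set number (which suggests there may be other sets) and the 12:18 split all leave that open.

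Thirdly, the baseline measures would reveal some imbalance, the exclusions narrow the range of men who could be steered, and this is a pilot.

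All of this stands as a limit on the claim, but it does not remove the gap. If the printed sequence is live, it is readable; if it is not, another fixed list exists and no described step hides it. Baseline data are collected after assignment and do not include motivation, so they would show only part of any imbalance.

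**Conclusion.** The point holds as a risk: allocation concealment is not described, a coded sequence of full trial length is printed, and as written those enrolling men could know the next arm. The documents do not show that anyone did know it, that the printed sequence is in use, or that men were steered. It would also be too strong to say that selection could never be told apart from an exercise effect, since part of any imbalance would show at baseline.

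The 0.16 to 0.48 SD range rests on an assumed f of 10% to 30%, error-free sorting at the median and a normal trait. It concerns the trait only, and imperfect sorting would make it smaller. This is a cheap improvement. It is worth making before enrolment, because concealment cannot be restored afterwards.

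**What to change.** In Section 5.3:
- Remove the printed sequence and state that it will not be used.
- Have a new 1:1 list generated and held by existing staff who do not recruit, consent or assess. The quality-assurance staff named in Section 9.1 are one possibility.
- Make the list consistent with 15 per arm in Section 4.1, and keep any block sizes from recruiters. An unrestricted list gives exactly 15:15 with probability only 0.14, so some restriction is needed. Because assignments become known, small blocks are the easiest to guess.
- Release each assignment singly, by sequentially numbered opaque sealed envelope or locked electronic module, only after consent is signed and the study number is logged.

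The cost is one rewritten paragraph, 30 envelopes or an electronic module, and a few minutes of administration per man. Sample size, significance level and visit schedule do not change.
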